12. ANNEX 2: SUMMARY ON ELIMINATION CODES

Table 5Safety Sets

PD code	PD Description	Study Period	All Exposed Set	Overall Safety Set	Safety Set, Unsolicited AEs	Safety Set, Solicited AEs
	Exclusion code		EXPFL	SAFFL	SSUFL	SSSFL
1030	Study vaccine not administered AT ALL	Day 1 – Day 181	EXC	EXC	EXC	EXC
2150	Subject did not provide any post-vaccination unsolicited safety data	Day 1 – Day 181	None	None	EXC	None
2160	Subject did not provide any post-vaccination solicited safety data	Day 1- Day 7	None	None	None	EXC

EXC = excluded from this analysis set.

Table 6 Immunogenicity Sets

PD code	PD Description	Study Period	FAS Day 29	PP Day 29
	Exclusion code		FAS29FL	PPS29FL
1030	Study vaccine not administered AT ALL	All Study	EXC	EXC
2100.1	Serological results are not available at Day 1 for any of the serogroups	Day 1	EXC (for 4-fold rise only)	EXC (for 4-fold rise only)
2100.2	Serological results are not available at Day 29 for any of the serogroups	Day 29	EXC	EXC
2120.1	Obvious deviation from Laboratory Manual or error in laboratory data at Day 1 for any of the serogroups	Day 1	None	EXC (for 4-fold rise only)
2120.2	Obvious deviation from Laboratory Manual or error in laboratory data at Day 29	Day 29	None	EXC
1050	Randomization failure	Day 1 – Day 29	None	EXC
1070	Vaccination not according to protocol	Day 1	None	EXC
1040	Administration of forbidden vaccine	Day 1 – Day 29	None	EXC
2010	Subject did not meet entry criteria	Day 1 – Day 29	None	EXC
2040	Administration of forbidden medication	Day 1 – Day 29	None	EXC
2090.1	Day 1 blood draw performed out of planned visit window	Day 1	None	EXC (for 4-fold rise only)
2090.2	Day 29 blood draw performed out of planned visit window	Day 29	None	EXC

FAS = Full Analysis Set; PPS=Per Protocol Set; M=Month EXC = excluded from this analysis set.

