5.1.4. Full Analysis Set

FAS (Day 29)

All subjects in the All Enrolled Set who:

- are randomized;
- receive the study vaccination;
- provide an evaluable serum sample at Day 29 that has an available result for serogroup A (primary objective)/ for at least one serogroup (secondary objectives). For percentages of subjects with a ≥4-fold rise, a baseline (Day 1) and a Day 29 result for at least one serogroup will be needed.

In case of vaccination error, subjects in the FAS set will be analyzed "as randomized" (i.e., according to the vaccine a subject was designated to receive, which may be different from the vaccine the subject actually received).

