5.2.2. Elimination from Per Protocol Set (PPS)

5.2.2.1. Excluded subjects

A subject will be excluded from the PPS analysis under the following conditions (for more detailed exclusions by visit/day, refer to Section 12 (Annex 2).

Code	Condition under which the code is used	
900	Invalid informed consent or fraud data	
1030	Study vaccine not administered at all	
1050	Randomization failure	
1060	Randomization code was broken	
1070	Subjects were vaccinated with the correct vaccine but containing a lower volume / Vaccination not according to protocol	
1080	Vaccine temperature deviation	
1090	Expired vaccine administered	
1040	Administration of concomitant vaccine(s) forbidden in the protocol	
2010	Protocol violation (inclusion/exclusion criteria)	
2040	Administration of any medication forbidden by the protocol	
2090	Subjects did not comply with blood sample schedule	
2100	Serological results not available post-vaccination	
2120	Obvious incoherence or abnormality or error in data	

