5.2.2.3. Visit-specific censored Data

Data from visit x will be censored for the PPS analysis under the following conditions. The code ****.x will also be used to identify study withdrawal from day y.

Code	Condition under which the code is used
2120.1	Obvious deviation from Laboratory Manual or error in the laboratory
	data at Day 1
2120.2	Obvious deviation from Laboratory Manual or error in the laboratory
	data at Day 29
2090.1	Subjects did not comply with blood sample schedule at Day 1
2090.2	Subjects did not comply with blood sample schedule at Day 29

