6.4. Immunogenicity

6.4.1. Analysis of immunogenicity planned in the protocol

The primary analysis will be based on the per-protocol set for analysis of immunogenicity. If, in any study group and timepoint, the percentage of vaccinated subjects with serological results excluded from the per-protocol set for analysis of immunogenicity is 5% or more, a second analysis based on the Full Analysis Set will be performed to complement the per-protocol analysis.

GMTs, Between-group ratios of GMTs and within-group Geometric Mean Ratios (GMRs)

The hSBA titers at each visit will be logarithmically transformed (base10) to obtain approximately normally distributed data. For each *N. meningitidis* serogroup A, C, W and Y, GMTs will be calculated, with their associated two-sided 95% CIs, by exponentiating the corresponding log-transformed means and their 95% CIs.

The between-group ratio of hSBA GMTs and corresponding 95% CI, at each of Day 1 and Day 29 against *N. meningitidis* serogroups A, C, W and Y will be obtained by exponentiating the between-group mean differences in log-transformed titers and the corresponding 95% CIs at each of the specified timepoints.

Within each study group and for each serogroup, GMRs will be calculated at Day 29 versus Day 1. The GMRs and 95% CIs will be constructed by exponentiating the withingroup mean differences in log-transformed titers and the corresponding 95% CIs.

The mean differences will be obtained from an Analysis of Covariance (ANCOVA) including pre-vaccination titer (Day 1) as a covariate and with vaccine group and center (if applicable) as factors in the model.

Percentages of subjects with $a \ge 4$ -fold rise in post-vaccination hSBA (Day 29)

The percentage of subjects with $a \ge 4$ -fold rise in post-vaccination hSBA (at Day 29 compared to Day 1) and associated two-sided 95% Clopper-Pearson CIs will be computed by group and *N. meningitidis* serogroups A, C, W and Y. Differences in percentages and associated 95% CIs between study groups will be calculated using the Miettinen and Nurminen score method. [Clopper, 1934; Miettinen, 1985]

Percentage of Subjects with hSBA titer ≥8 and ≥LLOQ* (Day 1 and Day 29)

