6.4.2. Additional considerations

The ANCOVA is used to adjust for the potential baseline imbalance between study groups. The ANCOVA analysis will be performed for the primary endpoint.

In addition, an Analysis of Variance (ANOVA) model with vaccine group and center (if applicable) as factors will be fitted in order to compute the estimates (not adjusted for pre-vaccination titer) together with their associated 95% CIs by exponentiating the corresponding log-transformed means and their 95% CIs.

205343 (MENACWY CONJ-032 [V59_71]) Statistical Analysis Plan Amendment 1 Final

For the 'by country' subgroup analysis, the ANCOVA and ANOVA models will be fitted without country in the model.

Given the high likelihood of having centers with few subjects enrolled in the study; therefore, country will be used as a factor in the ANCOVA/ANOVA analyses instead of center.

Permutation test (sensitivity analysis on primary objectives)

Based on the covariate-adaptive vaccine assignment algorithm (see Section 14 (Annex 4)), the following permutation test [Wiens, 2006; Hasegawa, 2009 and Ernst, 2004] will be performed as a sensitivity analysis on the primary objective in the PPS.

For serogroup A, let $\mathbf{X} = (X_1, ..., X_N)$ the logarithmically-transformed hSBA titers for the ACWY_liq group and $\mathbf{Y} = (\mathbf{Y}_1, ..., \mathbf{Y}_N)$ the logarithmically-transformed hSBA titers for ACWY group at 1 month after vaccination. A non-inferiority permutation test can be obtained from a superiority permutation test on $\dot{\mathbf{X}} = (X_1 + \delta, ..., X_N + \delta)$ against $\dot{\mathbf{Y}} = (\mathbf{Y}_1, ..., \mathbf{Y}_N)$ with $\delta = 0.301 = -\log_{10}(0.5)$.

The original vaccine assignment algorithm Section 14 (Annex 4) will be used to rerandomize subjects belonging to the ACWY_Liq group and ACWY group (see step 2a) while keeping hSBA titers, covariates and entry order as observed. The procedure will be as follows:

- 1. Fit the ANCOVA model to obtain the test statistics T^* for the superiority of \dot{X} against \dot{Y} ;
- 2. Estimate the distribution of the corresponding test statistic with R=10 000 repetitions of the following two steps:
 - a. Re-randomize vaccine assignment of groups $\dot{\mathbf{X}}$ and $\dot{\mathbf{Y}}$ (original algorithm);
 - b. Re-fit the full ANCOVA model to re-obtain the test statistics T;

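### Does the SAP need a new rule because the Day 29 per-protocol set admits subjects without the Day 1 titer that the primary ANCOVA uses?

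*SAP*

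**What the plan says.** **Who is in the set.** For the primary objective, SAP 5.1.4 asks that a subject "provide an evaluable serum sample at Day 29 that has an available result for serogroup A (primary objective". A Day 1 result is required only for the 4-fold-rise percentages. The PPS (SAP 5.1.5) is a subset of the FAS and adds no Day 1 requirement.

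**Table 6 in Annex 2.** Three codes concern Day 1:

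| Code | Meaning | FAS | PPS |
|---|---|---|---|
| 2100.1 | "Serological results are not available at Day 1 for any of the serogroups" | 4-fold rise only | 4-fold rise only |
| 2120.1 | "Obvious deviation from Laboratory Manual or error in laboratory data at Day 1 for any of the serogroups" | None | 4-fold rise only |
| 2090.1 | Day 1 draw outside the window | None | 4-fold rise only |

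**Other rules on the same codes.** SAP 5.2.2.1 lists the parent codes as PPS exclusions but adds "for more detailed exclusions by visit/day, refer to Section 12 (Annex 2". SAP 5.2.2.3 opens with "Data from visit x will be censored for the PPS analysis under the following conditions" and names 2120.1 and 2090.1.

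**The model.** SAP 6.4.1 specifies an ANCOVA "including pre-vaccination titer (Day 1) as a covariate", and SAP 6.4.2 confirms: "The ANCOVA analysis will be performed for the primary endpoint". SAP 6.4.2 also plans an ANOVA without the Day 1 titer and a permutation test that re-fits the ANCOVA. SAP 11.2 and Protocol 10.5 both rule out replacing titers that are missing or cannot be evaluated.

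**The concern.** The SAP recognises that 4-fold rise needs a Day 1 value but does not say the same of the primary model. Read literally, the sole confirmatory test is assigned to the PPS and yet cannot use every member of it. No sentence says so, and the permutation check loses the same people.

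Three sections also describe a flagged Day 1 value differently: the subject is excluded, the visit is censored, or only 4-fold rise is affected. In the FAS, code 2120.1 shows None and the censoring rule is written for the PPS alone. A baseline recorded as a laboratory error could then enter the FAS ANCOVA, the Day 29 to Day 1 ratios and the seronegative subgroup.

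At stake would be precision in the primary comparison, agreement between the stated set and the analysed set, and the value of the FAS as a check on the PPS.

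**Working it through.** **1. Reproduce the plan's power.** Inputs from Protocol 10.3: 437 evaluable per arm, true ratio 0.8, margin 0.5, SD 0.929 on the log10 scale, one-sided 0.025.

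- Difference from the margin: log10(0.8) − log10(0.5) = 0.2041.
- Standard error: 0.929 × √(2/437) = 0.0628.
- Noncentrality: 0.2041 / 0.0628 = 3.25.
- Power (noncentral t): 90.0%. This matches the stated 90%.
- Enrolment: 486 × 0.9 = 437.4, so 486 per arm and 972 in total are also reproduced.

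**2. Power if Day 1 titers are missing.** The documents give no rate. Assume 2% or 5% of the 437, in addition to the 10% dropout allowance. The correlation of 0.3 between Day 1 and Day 29 log titers is also an assumption; it multiplies the SD by √(1 − 0.3²) = 0.954.

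| Day 1 missing (assumed) | n per arm in ANCOVA | Power, no covariate gain | Power, correlation 0.3 |
|---|---|---|---|
| 0% | 437 | 90.0% | 92.5% |
| 2% | 428 | 89.4% | 92.0% |
| 5% | 415 | 88.5% | 91.2% |

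If the 10% allowance already covers these losses, there is no shortfall against plan.

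**3. When complete-case ANCOVA still beats an unadjusted analysis of everyone.** The variance of the adjusted difference is proportional to (1 − r²) / [n(1 − m)], where m is the missing fraction. It stays below the unadjusted variance, proportional to 1/n, while m < r². At r = 0.3 that allows 9% missing.

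**4. What imputation would gain.** Simulations used 437 per arm, Day 1 missing at random, correlation 0.3 and true ratio 0.8, with 6,000 trials per case.

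- 2% missing: complete-case 92.3%, pooled-mean imputation 92.7%. Gain 0.4 points.
- 5% missing: complete-case 91.2%, imputation 92.3%, unadjusted ANOVA 90.4%. Gain from imputation 1.1 points.
- The mean estimated ratio was 0.80 throughout. At a true ratio of 0.5 with 5% missing (20,000 trials), one-sided error was 2.5% for complete-case and 2.6% for imputation.

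**5. Erroneous baselines left in the FAS ANCOVA.** In a second simulation, 0%, 2% or 5% of Day 1 values were replaced by noise unrelated to arm, at correlations of 0, 0.3 and 0.5 (2,000 trials each). With errors present, the mean log10 difference was off by at most 0.0026. With no errors at all it was off by up to 0.0032, so this is simulation noise. The largest rise in standard error was from 0.0544 to 0.0564 (5% errors, correlation 0.5).

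**6. How the loss could arise.** Protocol Table 4 requires the Day 1 draw before vaccination. Protocol Table 8 puts serogroup A first in testing priority, so scarce serum costs serogroup A last. Protocol 5.3 blinds the laboratory to treatment. The documents therefore point to few missing Day 1 serogroup A titers, and to losses unrelated to arm.

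**7. Reading the three sections together.** SAP 5.2.2.1 hands visit-level detail to Annex 2. Table 6 assigns set membership. SAP 5.2.2.3 says what happens to the value. On that reading, a flagged Day 1 value in the PPS is treated as missing, the subject leaves 4-fold rise, and the subject stays in the Day 29 set. These rules can operate together.

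**The case for a change.** The strongest reply is that this is the only confirmatory test, so the subjects entering it should be written down before unblinding and not inferred from a missing-data rule. Two programmers could differ on whether a flagged Day 1 value may serve as a covariate. Subjects lost only from the ANCOVA remain in the PPS, so they need not count toward the 5% trigger for the FAS analysis. ANCOVA and ANOVA would rest on slightly different people. The wording about any of the serogroups is also loose.

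Much of this is accurate as description. The SAP never states that the ANCOVA number may be below the PPS number, and a sentence to that effect would be tidier. Whether the tables print the model N cannot be judged, because SAP 10 keeps the layouts in files outside these documents.

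It does not lead to a different analysis. With a covariate in the model and no replacement of missing titers, complete-case fitting is the only course open. For code 2100.1, SAP 5.1.4 works on a result for at least one serogroup, so the natural meaning is that none is available; looseness remains mainly for 2120.1. In the FAS column, None means the subject is not excluded. The same entry stands against the Day 29 laboratory-error code, so it is the general FAS convention. It does not instruct anyone to analyse a known error, and SAP 11.2 already provides for measurements that cannot be evaluated.

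The stronger remedies cost more than they return. Pooled-mean imputation reverses an explicit rule in both documents for about a point of power. Blanking out-of-window Day 1 values in the FAS discards observed data that the FAS is meant to keep, and no harm from retaining them has been shown.

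**Conclusion.** The mismatch between PPS membership and the primary model is real but needs no amendment. It is a gap that an analyst fills in the one way the no-replacement rule allows. The primary comparison stays valid, and no bias is shown.

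The cost is a small loss of precision of unknown size. At an assumed 2% to 5% missing it is 0.6 to 1.5 power points with no covariate gain (90.0% to 89.4% or 88.5%). At an assumed correlation of 0.3, power stays above the planned 90%. The planning SD is already an upper confidence limit, by Protocol 10.3.

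The FAS point touches only a supportive analysis that runs if exclusions reach 5%, and the non-inferiority decision rests on the PPS (SAP 7.1). The conclusion assumes that Day 1 losses and errors are unrelated to arm, which the pre-vaccination draw and the blinded laboratory support.

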13. ANNEX 3: STUDY SPECIFIC MOCK TFL

The summaries are to include the following header:

GSK Biologicals	Vaccine: MenACWY (GSK3536820A and Menveo)
MenACWY CONJ-032 [V59_71]	Immunogenicity and Safety in Healthy Individuals 18-40 years

14. ANNEX 4: RANDOMIZATION METHOD AND MINIMIZATION ALGORITHM

The minimization algorithm used at the GSK internet randomization system (i.e. SBIR) is based on the following reference: "White SJ, Freedman LS. Allocation of patients to treatment groups in a controlled clinical study." [White, 1978] and is detailed in Section 14.1.

14.1. SBIR Algorithm V8.x

14.1.1. Introduction

This minimization algorithm is extracted from:

14.1.2. Minimization algorithm

14.1.2.1. Notations

- K input values to be used for minimization, each with a weight w_k (k=1,.., K) & l_k variants
- I treatment groups applicable to stratum the subject has been identified with randomization ratio **a**₁,... **a**₁

14.1.2.2. Algorithm

For a new subject with input value levels S1,.... SK

For each input value variants sk:

[figure not shown]
- Compute the number of subjects already enrolled in each treatment in the identified stratum.
 - Let **bik** the total number of subjects in the identified stratum already randomized in treatment I and in input value variant k.

For each treatment i: compute $A_i = 1/a_i * \text{sum}_k(w_k * b_{ik})$

Where A_i is the minimization value for treatment **i**.

14.1.3. Study group selection

14.1.3.1. Process flow

14.1.3.2. Study Group identification algorithm

The seed used to initialize randomization engine must take into account date time till microsecond, this will ensure uniqueness of the seed for each subject.

This seed is to be recorded along with randomization data of the subject.

1. Determine whether the algorithm is deterministic or not:

- Generate R, a random number within [0-1], uniform distribution.
- If R < % determinism parameter

then

group allocation will be deterministic go to (2)

else

it will be at random go to (3).

2. Group allocation is deterministic:

- Order treatment groups, which can be allocated to the subject according to his stratum, by minimization value,
- If more than 1 group have the same minimization value then select at random a treatment group amongst them, randomization ratio must be equal for each of these groups.
- If this is the 1st iteration then this group is identified as the "randomized" group,
- Go to step (4).
- 3. Group allocation is at random:
- Retrieve list of treatment groups and ratio which can be allocated to the subject according to his stratum,
- Select at random one of the treatment groups, randomization must follow study ratio.
- If this is the 1st iteration then this group is identified as the "randomized" group.
- 4. Check for treatment No(s). dedicated to the 1st vaccination time point for the selected treatment group.
- Check vaccination schedule of the selected group for the subject's stratum in order to identify:
 - the type of treatment No(s) to be allocated
 - the list from which these treatment No(s) should be extracted depending if center using ordering system or not.

- For each type of treatment for which a treatment No. must be identified:
 - The treatment No(s) to be selected must have an expiry date greater than the planned vaccination date entered for subject.
 - In case multiple injections can be extracted from 1 treatment No. then first used the "opened" treatment Nos.
 - The treatment Nos. must be selected starting by the ones expiring first, then by the one first received in the stock to be used for allocation, then on the block id's.
 - In case "Ordering system" is activated on the center without "Randomization pool", check the stock according to below order:
 - i. Center stock
 - In case "Ordering system" is activated on the center with "Randomization pool", check the stock according to below order:
 - i. Randomization pool
 - In case "Ordering system" is not activated on the center, check the stock in according to below order:
 - i. Center stock
 - All the treatment No(s) to be allocated to the subject must be issued from the same stock.
- 5. If it was not possible to allocate all the necessary treatment No(s) from the stocks, then :
- The identified treatment No(s) are sent back to the stock they have been identified
- The selected treatment group is removed from the possible treatment group
- If there are still treatment group on which to iterate,

then

algorithm must start new iteration at (2 or 3, depending on determinism),

else

an error message must be issued.

Else:

• The selected treatment group is identified as the "allocated" group.

gsk GlaxoSmithKline	Statistical Analysis Plan		
Detailed Title:	A phase 2b, randomized, controlled, observer-blind, multi-center, non-inferiority immunogenicity and safety study of two formulations of GSK Biologicals' Meningococcal ACWY conjugate vaccine (GSK3536820A and Menveo) administered to healthy adults 18 to 40 years of age.		
eTrack study number and Abbreviated Title	205343 (MENACWY CONJ-032 [V59_71])		
Scope:	All data pertaining to the above study.		
Date of Statistical Analysis Plan	Final: 29 AUG 2018		
Co-ordinating author:	(Biostatistician)		
Reviewed by:	PPD (Lead statistician) PPD (Lead statistical analyst) PPD (Clinical and Epidemiology Research and Development Project Lead) PPD (Clinical Research and Development Lead) PPD (Scientific writer) PPD (Regulatory Affairs representative) PPD (Clinical Safety representative) PPD (Public disclosure representative) PPD (Lead statistician)		
Approved by:	PPD (Lead statistician) PPD (Lead statistical analyst) PPD (Clinical and Epidemiology Research and Development Project Lead) PPD PPD (Clinical Research and Development Lead) PPD PPD (Scientific writer)		

TABLE OF CONTENTS

PAGE

LIS	T OF A	BBREVIA	TIONS		6
1.	DOCUMENT HISTORY8				
2.	STUDY DESIGN				8
3.	OBJE(3.1. 3.2.	- , - ,			10
4.	ENDP 4.1. 4.2.	Primary e	endpoint	s	11
5.	5.1.	Definition 5.1.1. 5.1.2. 5.1.3. 5.1.3. 5.1.4. 5.1.5. 5.1.6. 5.1.7. Criteria fo 5.2.1. 5.2.2. Importan	All Enrolled All Expose Safety Set 5.1.3.1. 5.1.3.2. 5.1.3.3. Full Analys Per Protoc Other Anal Subgroups or elimination Elimination 5.2.2.1. 5.2.2.3. t protocol d	· · · · · , · · · ,	12 12 12 12 12 12 12 12 12 13 13 13 13 13 13 14 14 14 15
6.	STATI 6.1.		phy Analysis o	f demographics/baseline characteristics planned ocol	15

SAP	Statistical Analysis Plan
SBIR	GSK Biologicals Internet Randomization System
SD	Standard Deviation
SR	Study Report
TFL	Tables Figures and Listings

[figure not shown]
- TOC Table of Content
- UL Upper Limit of the confidence interval
- YoA Years of Age

1. DOCUMENT HISTORY

Date	Description	Protocol Version
29-AUG-2018	First version	Protocol Amendment 2: 15-MAR-2018

2. STUDY DESIGN

Figure 1 Study design overview

* At Visit 1, blood samples will be taken pre-vaccination

- Experimental design: Phase IIB, observer-blind, randomized, controlled, multicentric study with two parallel groups.
- Duration of the study: for each subject enrolled, the duration will be approximately 6 months.
 - Epoch 001: starting at Visit 1 (Day 1) and ending at last Safety contact (Day 181).
- Primary completion Date (PCD): Visit 2 (Day 29).
- End of Study (EoS): Last subject last visit(LSLV) (Phone call 3 Day 181) or last testing results released of samples collected at Visit 2 (Day 29)* if it occurs after LSLV.

*In this case EoS must be achieved no later than 8 months after LSLV.

- Study groups:
 - Group ACWY_Liq: ~486 healthy adults receiving a single dose of investigational liquid MenACWY (GSK3536820A) with approximately 30% Men A FS.

- **Group ACWY**: ~486 healthy adults receiving a single dose of currently licensed GSK' MenACWY vaccine (Menveo).

Table 1Study groups and epochs foreseen in the study

Study groups	Number of subiects	Age (Min/Max)	Epochs Epoch 001
ACWY_Liq	~486	18 – 40 years	X
ACWY	~486	18 – 40 years	х

Table 2Study groups and treatment foreseen in the study

T t t	Vaccine/product	Study Groups		
Treatment name	name	ACWY_Liq	ACWY	
MenACWY liquid with approximately 30% MenA FS	MenACWY liquid	X		
Licensed MenACWY (Menveo *)	MenA lyo MenCWY liquid		x	

* *Menveo* commercial formulation consisting of a MenA lyophilized component and a MenCWY liquid component to be reconstituted together before administration (0.5mL).

- Control: active control
- Vaccination schedule: All subjects will receive a single dose of one of the study vaccines at Visit 1 (Day 1).
- Treatment allocation: Subjects will be randomized using a centralized randomization system on internet (SBIR) at Visit 1 (Day 1).
- Blinding: observer-blind.
- Sampling schedule: Blood samples of approximately 20 mL will be taken at Visit 1 (Day 1; pre-vaccination) and Visit 2 (Day 29).
- Type of study: self-contained.
- Data collection: Standardised Electronic Case Report Form (eCRF). Solicited adverse events (AEs) assessed on site during the 30 minutes post-vaccination assessment are to be recorded on the source documents and entered in the eCRF. Solicited AEs occurring after the 30 minutes post-vaccination assessment will be collected only using a subject Diary (electronic Diary [eDiary]).

Table 3 Intervals between study visits

Interval	Optimal length of interval	Allowed interval
Visit $1 \rightarrow$ Phone call 1	14 days	11 - 17 days
Visit 1 \rightarrow Visit 2	28 days	21 - 42 days
Visit 1 \rightarrow Phone call 2	90 days	76 - 104 days
Visit 1 \rightarrow Phone call 3	180 days	166 - 194 days

